**NCT Number: NCT05435885**

**Document Date: May 28, 2025**

## ***STUDY DESIGN***

This was a multicenter, parallel-group, RCT with concealed allocation and assessor blinding. All procedures performed in studies involving human participants were in accordance with the ethical standards of the institutional research committee and with the 1964 Declaration of Helsinki and its later amendments or comparable ethical standards. The study was approved by the Institutional Review Boards of Pusan National University Hospital (2205-033-114) and Pusan National University Yangsan Hospital (05-2022-143) and was registered with ClinicalTrials.gov (NCT05435885). All participants provided written informed consent.

## ***SETTING AND PARTICIPANTS***

Patients aged  $\geq$  65 years with lung cancer scheduled for VATS were recruited. The exclusion criteria included patients with limited ambulation requiring an assistive device due to musculoskeletal disorders or cerebral infarction, those with implanted medical devices, individuals unable to use mobile messenger applications, and those participating in other clinical trials assessing exercise capacity.

## ***SAMPLE SIZE AND RANDOMIZATION***

The sample size was calculated using G\*Power (version 3.1.9.6) based on an estimated between-group difference in  $\text{VO}_{2\text{peak}}$  of 3.4 mL/kg/min after the intervention. This estimate was derived from previously published data, where the post-intervention  $\text{VO}_{2\text{peak}}$  values were 23.3 mL/kg/min in the exercise group and 19.0 mL/kg/min in the control group. A power analysis using an effect size of 0.74, a significance level of 0.05, and power of 0.80 determined the required sample size. Based on a power analysis, the required number of participants was 60. To account for an anticipated dropout rate, we screened 96 patients. A total of 64 participants were ultimately randomized. Participants were randomly assigned 1:1 to an intervention group (IG) or a control group (CG) using a central randomization method.

A single individual, uninvolved in the study, managed the process to ensure allocation concealment. An independent statistician generated a randomization table using the R package “blockrand” (version 4.1.3). The block size and seed number were blinded before being provided to the randomization manager. To maintain balance between the groups, a blocked randomization method was chosen, considering the small sample size. Equal block sizes were used across all sites to ensure consistency in the allocation process.

### ***INTERVENTION PROTOCOL***

The intervention, Home-Based Pulmonary Rehabilitation Program with Telerehabilitation Support (HBPR-TS), combines traditional pulmonary rehabilitation with digital health support to enhance adherence and outcomes. Designed for post-lung surgery patients, it addresses challenges in maintaining home rehabilitation. Given the high risk of postoperative pulmonary complications, it aims to improve respiratory function, enhance exercise capacity, and support adherence to prescribed rehabilitation through structured home exercises and remote monitoring. By combining in-person education with telemonitoring via instant messaging, the program may provide real-time feedback and individualized support, fostering better long-term outcomes.

#### ***Preoperative and immediate postoperative respiratory training***

Breathing exercises and respiratory muscle training (RMT) were performed before and immediately after surgery using an incentive spirometer (SPIRO-BALL®; Leventon) and a threshold respiratory muscle trainer (IMT/PEP; GH INNOTEK). Participants initiated RMT at 30% of maximal inspiratory pressure (MIP), gradually increasing to 50% as pain subsided. Each session included 10 repetitions per set, with a total of 10 sets performed daily. This preoperative intervention aimed to enhance respiratory function and reduce the risk of postoperative pulmonary complications.

#### ***Postoperative home-based PR program***

At 4 wk post-surgery (baseline), both groups attended a one-time educational session on standardized home-based PR, conducted by a respiratory physiotherapist at the rehabilitation center. The program was delivered through an educational booklet (Appendix file), which provided detailed information on the rationale, procedures, and precautions for each exercise. Furthermore, QR codes linking to instructional photographs and videos were included. The PR program comprised flexibility exercises, aerobic exercises, resistance training, and continued RMT.

Flexibility exercises targeted limb and trunk mobility, performed three times per week. Stretching intensity was self-paced, held for 10 to 15 sec per stretch, and repeated three times per session. Participants performed neck and arm stretches while seated and leg stretches while standing. For aerobic exercise, a recumbent cycle ergometer (706R; Egojin), installed at each participant's home, was used. Sessions occurred three times per week for 40 minutes, including warm-up and cool-down phases. Intensity was based on cardiopulmonary exercise testing (CPX), starting at 40% of heart rate reserve (HRR) and progressing to 70% of HRR, monitored using a fitness tracker (Galaxy Fit2; Samsung). Resistance training consisted of upper and lower limb strengthening exercises using adjustable elastic bands (TheraBandTM; Akron). Participants performed resistance exercises three times per week, with three sets of 15 repetitions per exercise. Respiratory muscle training continued postoperatively using an IMT/PEP device. Participants started at 30% of MIP, increasing to 50% as pain decreased. Each session included 10 repetitions per set, with 10 sets daily.

#### ***Postoperative telerehabilitation (PTR) program IG only***

The IG group received PTR support via a mobile instant messaging application (KakaoTalk; Kakao) three times per week for 4 wk. The PTR program monitored adherence, provided feedback, and adjusted exercise intensity as needed. When retraining or exercise intensity adjustment was needed, education was delivered via text messages, photos, or videos through

a mobile messenger. For participants unfamiliar with the designated mobile messenger, the app was installed and training was provided, considering digital literacy challenges often observed in older adults. However, if participants still had difficulty using the messenger despite training, phone calls were used instead. Two respiratory physiotherapists provided remote supervision through weekly structured messages. The specific instructions and questions provided via messenger included the following:

- 1) Have you achieved your prescribed exercise goals over the past 2 days?
- 2) Was the target heart rate on the fitness tracker maintained well during aerobic exercise?
- 3) Were there any difficulties while performing each exercise?
- 4) Did you write a self-exercise diary after completing the exercise?
- 5) Do you have any further questions?

### ***CG intervention***

Participants in the CG received a second educational session at 8 wk post-surgery at the rehabilitation center. Apart from these two educational sessions, no further communication was provided. Both groups were instructed to maintain their prescribed exercise routines at least three times per week during the 4-wk follow-up period.

### ***OUTCOME MEASURES***

Outcomes were assessed at four time points in the two rehabilitation centers: preoperatively and at 4 (baseline), 8 (post-intervention), and 12 wk (follow-up) postoperatively. Primary outcomes included VO2peak and predicted VO2peak %, calculated using Hansen's formula based on CPX performed on a treadmill using a cardiac stress system (Q-Stress; Mortara) with a treadmill (TM-55; Mortara). Gas exchange analysis was performed using a metabolic cart (Quark CPET; Cosmed). Secondary outcomes included ventilatory efficiency (VE/VCO2 slope), forced vital capacity (FVC), forced expiratory volume in 1 sec (FEV1), peak expiratory flow (PEF), MIP, grip strength, skeletal muscle index (SMI), body mass index

(BMI), and whole-body phase angle. SMI and whole-body phase angle were measured using a bioelectrical impedance analysis device (S10; InBody) with electrodes attached to the wrist and ankle after 3 minutes of supine rest. The SMI was calculated by dividing skeletal muscle mass (kg) by height squared (m^2). FVC, FEV1, PEF, and MIP were assessed using a desktop spirometer (Pony FX; Cosmed) following standardized procedures. Grip strength was measured using a handheld dynamometer (Jamar Plus+, Sammons Preston). Psychological well-being and quality of life were assessed using the Hospital Anxiety and Depression Scale (HADS) and the EuroQol 5-dimension questionnaire (EQ-5D-5L). Adherence to the home-based PR program was recorded in a diary. Daily step counts were recorded using a fitness tracker and extracted from the Samsung Health app on each participant's personal mobile phone. To minimize measurement errors, the average step count was calculated for each week, excluding days with the highest and lowest step counts.

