### ***STATISTICAL ANALYSIS***

An independent t-test or Wilcoxon rank-sum test was used to compare groups at each time point. Categorical variables were compared using the Chi-square test or Fisher's exact test. Within-group comparisons were performed using paired t-tests. To appropriately account for repeated measurements and missing data, a Linear Mixed Model (LMM) was employed for the primary outcomes (VO2peak and VO2peak%), allowing for unbiased parameter estimation under the Missing At Random (MAR) assumption. Missing data were handled using maximum likelihood (ML) estimation within the LMM framework. Statistical analyses were conducted using R (version 4.2.1; R Core Team). A two-tailed  $P \leq .05$  was considered significant.

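### Two primary outcomes, two post-baseline visits and two kinds of test each count at P ≤ .05, with no deciding test, while the sample size covers one comparison

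*Combined protocol and SAP*

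**What the plan says.** - **Sample size (SAMPLE SIZE AND RANDOMIZATION).** The trial is sized on one quantity, the between-group difference in VO2peak once the intervention has ended: "A power analysis using an effect size of 0.74, a significance level of 0.05, and power of 0.80 determined the required sample size". The required number is 60, and "A total of 64 participants were ultimately randomized".
- **Outcomes (OUTCOME MEASURES).** "Primary outcomes included VO 2 peak and predicted VO 2 peak" as a percentage. There are four assessments. The two that follow the start of telerehabilitation support in the intervention group are described as "8 (post-intervention), and 12 wk (follow-up) postoperatively".
- **Analysis (STATISTICAL ANALYSIS).** "An independent t-test or Wilcoxon rank-sum test was used to compare groups at each time point". A linear mixed model "was employed for the primary outcomes (VO 2 peak and VO 2 peak" %). One threshold, two-tailed P ≤ .05, applies throughout.

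None of these sections designates a primary time point, an LMM contrast, which analysis decides if the LMM and the per-visit test disagree, an order of testing, a division of alpha, or a rule that both outcomes must succeed.

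**The concern.** The design spends its 5% error on one comparison, but the analysis allows several results to be called the primary finding. As written, a significant P value for either outcome, at week 8 or week 12, could be reported as a positive primary result. Each test keeps its own 5% level, and the documents promise no trial-wide rate, so no stated commitment is broken. The problem is that nothing limits how many results may count. The chance of at least one false-positive primary result is then above the 0.05 used to size the trial, and a reader cannot tell which result was meant to decide it.

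**Working it through.** **1. Reproduce the planned sample size.** Inputs from the sample size section: d = 0.74, alpha 0.05, power 0.80, 1:1 allocation. The two-sided threshold comes from the analysis section.

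- Normal approximation: n per arm = 2(1.960 + 0.842)² / 0.74² = 28.7, so 29 per arm, N = 58.
- Noncentral t (noncentrality d√(n/2), 2n − 2 degrees of freedom): n = 29.66, so 30 per arm, N = 60. This matches the plan exactly.
- A one-sided t-test would give 48, which does not match.

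So 60 is the number for one two-sided test at 0.05, with no allowance for a second outcome or visit.

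**2. Count the routes to a positive primary result.** The preoperative and week-4 comparisons come before the support given only to the intervention group, so they are not counted. That leaves 2 outcomes × 2 visits = 4 per-visit tests. LMM results are not added in step 4 because the plan does not name their contrast.

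**3. Upper reference, independent tests.**

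- Two tests: 1 − 0.95² = 9.75%.
- Four tests: 1 − 0.95⁴ = 18.5%.

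The real tests are positively correlated, so the true rates are lower.

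**4. Correlated tests, by simulation with no effect.** Multivariate normal data, 32 per arm, two-sided t-tests, no dropout, 40,000 replicates in each of 12 scenarios. Assumed correlations: 0.6, 0.8, 0.9 or 0.95 between outcomes, and 0.6, 0.75 or 0.9 between visits.

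| What may count as primary success | All scenarios | Outcome correlation 0.9–0.95 only |
|---|---|---|
| Either outcome, week 8 | 6.3–8.8% | 6.3–7.1% |
| VO2peak alone, week 8 or 12 | 7.0–8.8% | not applicable |
| Either outcome, week 8 or 12 | 9.0–15.1% | 9.0–12.0% |
| Fixed sequence at week 8 (VO2peak, then VO2peak %) | 4.9–5.2% | – |

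A separate normal-theory calculation agrees. Two tests with correlation 0.7, 0.8, 0.9 and 0.95 give 8.3%, 7.8%, 7.1% and 6.5%. Four tests with outcome correlation 0.7–0.95 and visit correlation 0.5–0.9 give about 9–15%.

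**5. If the LMM is the only analysis that counts.** Assume its contrasts behave like tests of change from week 4. Either outcome at week 8 then gives 6.4–9.2%, and either outcome at week 8 or 12 gives 11.2–16.2%. A free choice between the t-test and such a contrast, for one outcome at week 8, gives about 9–10%.

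**6. Power of the possible remedies** (t-test, d = 0.74, everyone analysed).

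| Alpha for the test | N = 60 | N = 64 | N for 80% power |
|---|---|---|---|
| 0.05 (one deciding test, or first in a sequence) | 80.5% | 83.0% | 60 |
| 0.025 (Bonferroni, two outcomes) | 71.3% | 74.5% | 74 |
| 0.0125 (Bonferroni, two outcomes × two visits) | 61.5% | 65.1% | 86 |

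With the fixed sequence at N = 64, and d = 0.74 assumed on both outcomes, power is 83% for VO2peak and 73–80% for both.

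**The case against.** The strongest reply has four parts.

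- **Week 8 is implied.** The sample size refers to the end of the intervention, the outcomes section attaches that label to week 8 alone, and week 12 is called follow-up. On that reading 6.3–8.8% is the relevant range and 9.0–15.1% is a conditional worst case. This is fair, but a label does not make week 8 the deciding visit, and the analysis section tests every visit at the same threshold.
- **The two outcomes are nearly one measurement.** Both come from the same exercise test, so their correlation is plausibly high. At 0.9–0.95 the week-8 excess is only about 1 to 2 percentage points. That stands. Even at 0.99, however, either outcome at week 8 or 12 still gives 8.0–10.1%, because the open time point adds inflation of its own.
- **The LMM is the natural main analysis.** The plan assigns it to the primary outcomes, and a single group-by-time test per outcome would not multiply over visits. But no such test is named, two outcomes would remain, and step 5 shows that visit-specific LMM contrasts do not remove the inflation.
- **The remedy comes late and its power is approximate.** The document is written in the past tense and carries "Document Date: May 28, 2025". The 4.9–5.2% rate holds only if the order was set without knowledge of results. The power figures are for a t-test with no dropout: with 54 analysed, for illustration, power is 76%. LMM power has not been computed. These limits stand and are carried into the fix.

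**Conclusion.** The concern holds. That the plan has no deciding primary test is certain from its text; the size of the inflation is less certain. If only week 8 counts, the false-positive rate is 6.3–8.8%, and probably in the lower part of that range given how closely the two outcomes are related. If week 12 can also count, it is 9.0–15.1%. These figures assume outcome correlations of 0.6–0.95, visit correlations of 0.6–0.9, normal data, no dropout and 32 per arm. The inflation is moderate and does not invalidate the trial, but it should be fixed: the plan's own significance rule, applied to both primaries, exceeds the 5% on which the sample size was built.

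**What to change.** In OUTCOME MEASURES and STATISTICAL ANALYSIS:

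1. Name the LMM between-group contrast for VO2peak at 8 weeks, two-sided 0.05, as the deciding primary test. It is the comparison the sample size was built on.
2. Test VO2peak % at 8 weeks at 0.05 only if the first test succeeds, which keeps both primaries. Alternatively, make it secondary.
3. Treat week-12 results as secondary, and the per-visit t-test or Wilcoxon results for these two outcomes as descriptive.
4. Date and disclose the designation, and say whether it was made before results were known. If not, label it post hoc and do not claim the 5% error rate for it.
5. Report both outcomes at both visits whatever they show.

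**Cost.** Two or three sentences and a dated disclosure. The sample size and the planned t-test power for VO2peak are unchanged, whereas a Bonferroni split over the two outcomes would lower power to 71.3% at 60 or 74.5% at 64. The price is that VO2peak % alone, or a week-12 result alone, can no longer make the trial positive.

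### Does asking only the intervention group whether it kept its exercise diary call for a change to the adherence analysis?

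*Combined protocol and SAP*

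**What the plan says.** The INTERVENTION PROTOCOL section says the program "combines traditional pulmonary rehabilitation with digital health support to enhance adherence and outcomes", so better adherence is one of its stated purposes. OUTCOME MEASURES then says only that "Adherence to the home-based PR program was recorded in a diary". Adherence appears in neither the list of primary outcomes (VO2peak and predicted VO2peak %) nor the list of secondary outcomes.

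The section on the postoperative home-based program gives both arms the same start: "both groups attended a one-time educational session on standardized home-based PR", with a booklet that is cited as an appendix. It also sets the prescription: "The PR program comprised flexibility exercises, aerobic exercises, resistance training, and continued RMT". The frequencies are given component by component:

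- flexibility: "Flexibility exercises targeted limb and trunk mobility, performed three times per week"
- aerobic: "Sessions occurred three times per week for 40 minutes, including warm-up and cool-down phases"
- resistance: "Participants performed resistance exercises three times per week"
- respiratory muscle training: "Each session included 10 repetitions per set, with 10 sets daily"

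The telerehabilitation section applies to the intervention group (IG) alone. The fourth of its five message questions asks whether the participant wrote the diary after exercising. Contact is put at thrice weekly over four weeks in one place and at weekly in another. The section on the control group (CG) adds a second session at week 8 and rules out any other contact.

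STATISTICAL ANALYSIS gives a generic two-group test (t-test or Wilcoxon) at each assessment and a linear mixed model for the two VO2peak outcomes. It does not mention adherence.

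**The concern.** In weeks 4 to 8 the randomized treatment acts on the instrument that would measure adherence. One arm is reminded to write in its diary and tells its therapists whether it met its goals; the other arm hears nothing. Randomization balances patients, not reminders sent after allocation, and assessor blinding does not reach a record that the participant fills in.

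Since raising adherence is a stated purpose, a higher IG diary rate could be taken as proof that the program worked. It might instead show fuller recording, more favourable reporting, more exercise, or a mix of these. The documents shown give no denominator, no rule for blank entries and no check of the diary against a device. The step counts do not supply such a check, because the prescribed aerobic work was on a recumbent cycle and the rest was stretching, elastic bands and breathing training. At stake is one inference: that telerehabilitation raised exercise adherence during the intervention period.

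**Working it through.** **The plan's own figure.** The plan gives no number for adherence. Its one design figure, 60 participants, concerns VO2peak. A two-sided two-sample t-test with effect size 0.74, alpha 0.05 and power 0.80 needs 29.66 per arm, rounded up to 30, so 60 in total. The figure reproduces, and adherence plays no part in it.

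**Described prompts** (telerehabilitation and CG sections).

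- Weeks 4 to 8, IG: 3 × 4 = 12, or 1 × 4 = 4 on the weekly reading. CG: 0.
- Weeks 8 to 12: 0 in both arms.

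The asymmetry holds on either reading, but only for weeks 4 to 8.

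**Prescribed sessions over 4 weeks** (home-based program section).

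- Flexibility, aerobic and resistance: 3 × 4 = 12 each, 36 together.
- Respiratory muscle training: 7 × 4 = 28.
- Total if counted separately: 36 + 28 = 64.

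**Scale of a recording gap.** Assume equal true exercise in both arms and blanks counted as not done. The spurious difference is then the net number of unwritten units divided by the denominator. The gap sizes below are assumptions; the documents give none.

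| Unit | Net gap −1 | 0 | +1 | +2 |
|---|---|---|---|---|
| Component-session (1/64) | −1.6 | 0 | +1.6 | +3.1 |
| Day with all four components (4/64) | −6.25 | 0 | +6.25 | +12.5 |
| Aerobic session only (1/12) | −8.3 | 0 | +8.3 | +16.7 |

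Entries are percentage points, IG minus CG. A gap of −2 mirrors the last column. The second row also assumes that the three thrice-weekly components fall on the same days, which the plan does not say.

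A second illustration uses assumed recording rates: apparent difference = true adherence × (IG recording rate − CG recording rate).

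- True adherence 60%, rates 95% and 85%: 0.60 × 0.10 = 6 points, or 0.72 of 12 sessions.
- True adherence 80%, rates 95% and 65%: 0.80 × 0.30 = 24 points, or 2.88 of 12 sessions.
- Equal rates: 0.

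These results follow from the assumed inputs and the undefined unit. They show that an effect is possible, not that one occurred.

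**What each possible change would achieve.**

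- *Label adherence descriptive and drop the test.* No adherence test is specified. The generic comparison is tied to assessment visits, whereas adherence accumulates over a period. A by-arm table without a P value carries the same recording difference.
- *Count blanks as missing.* If participants write only completed sessions, which the wording of the fourth question allows, both arms read 100% and the difference is 100% − 100% = 0. The analysis then says nothing.
- *Report diary completeness by arm.* With that type of diary, completeness and recorded adherence are the same quantity, so nothing is separated. It helps only if the form distinguishes a session not done from a blank, and the form is not shown.
- *State a denominator and a blank-entry rule.* This is useful detail, but an analyst would settle it when tabulating, and the booklet or diary form may already do so.
- *Check against the tracker.* The home-based section has both arms monitor aerobic intensity with a tracker, but only step-count extraction is documented. The plan cannot rest on session records that may not exist.

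**The case for a change.** The strongest case for acting is that the flaw is structural and the remedy nearly free. Adherence is collected under OUTCOME MEASURES, the program is meant to raise it, and nothing in the analysis section excludes it from the generic between-group test. Equal instruction at week 4 would not equalize later reminders. A bias of unknown size is a reason to forgo a formal claim, and the only cost is a claim the design cannot support.

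Most of the factual part stands. The prompting is one-sided for four weeks, and the diary alone may not tell extra exercise from extra recording. Reminders and self-monitoring are, however, part of the treatment being compared. Some effect on a self-kept record comes with this design and would remain under any analysis wording. What stands is a caution about interpretation: a higher IG diary rate should not be presented on its own as evidence that the program raised adherence. If the form marks sessions as not done, showing the share of blanks by arm, with blanks counted both ways, would be sensible reporting. The two message frequencies in the telerehabilitation section need reconciling, but that is a separate matter and does not alter this point.

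**Conclusion.** No change to the plan follows. The difference in diary prompting is real, confined to weeks 4 to 8, and bears only on a between-group reading of diary adherence, which the plan neither names as a primary or secondary outcome nor assigns to a test. The primary comparison does not depend on it. The trial-specific effect cannot be computed, and even its direction is open; the illustrative figures rest on assumed recording gaps or rates, on counting blanks as not done, and on a choice of denominator that the documents do not make.

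The conclusion assumes that adherence is reported as supporting information. If a report rested an efficacy claim on diary adherence, that claim would deserve challenge, but the fault would lie in the report and not in the plan as written.
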